One data collection form will use a research number and CCF medical record number; as it will also contain names and phone numbers; however, all other baseline and follow-up data collection forms contain only research numbers. Only the research number will be recorded in the electronic database. Paper forms will be kept in a locked cabinet, in a locked office of the principal investigator and will be destroyed upon assurance that data in the electronic database is high quality, after enrollment is completed. Electronic data for analysis will use a research number; no patient identifiers will be used. All study results will be reported in aggregate.

NCT-03657459

SPSS will be the electronic database used to capture paper data. The electronic database will be maintained for 6 years after study completion. Paper documents will be destroyed once the initial analysis is complete.

This research project will be registered in www.clinicaltrials.gov.

References

4. van der Wal MH, van Veldhuisen DJ, Veeger NJ, Rutten FH, Jaarsma T. Compliance with non-pharmacological recommendations and outcome in heart failure patients. *Eur Heart J*. 2010;31:1486-93.

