The most frequently cited danger signs of heart failure (HF) are new onset or worsening of fatigue, dyspnea and edema. In previous research, patients did not recognize worsening HF, due to 3 primary reasons: (1) danger signs were non-specific and misinterpreted as stress, an external force or another comorbidity, (2) danger signs were unrecognized due to the subtle nature of worsening status, or (3) when patients eliminated or minimized activities that prompted danger signs, they interpreted the results as improvement in status. Lack of recognition of HF danger signs and lack of understanding of how to control and minimize danger signs could lead to their escalation and prompt all-cause and HF-related health care resource utilization (HCRU: emergency department care, hospitalization, death/ventricular assist device/cardiac transplantation referral or placement, or an unscheduled/urgent office visit). During hospitalization, patient education is delivered, but it is assumed that patients understand the danger signs and simply need education in self-care behavior expectations. We hypothesize that patients must understand HF danger signs to have self-confidence in recognizing them and in taking steps to minimize or eliminate their occurrence post hospital discharge. Therefore, the purposes of this randomized, controlled trial are to determine if video education in HF danger signs recognition and control prior to discharge and post-discharge reduces all-cause and HF-related 30-, 60-, 90- and 180-day HCRU. Research nurses will deliver the intervention during hospitalization, and patients and family members will receive a link to a website and a DVD of content to review videos as often as desired post-discharge. The primary end-point is 30-day HF-related HCRU. A total of 732 patients (658 + 10% attrition) with decompensated HF will be enrolled. Patients will be followed by telephone or medical record review to determine HCRU post index hospitalization.

INTRODUCTION

Chronic heart failure (HF) is a costly diagnosis;¹ especially for patients who are hospitalized due to decompensation. Heart failure decompensation and hospitalization place patients at high risk for rehospitalization, exacerbating costs of care and potential penalties associated with the Patient Portability Affordable Care Act.²

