It is unknown if in-hospital video education (with repeat viewing post-discharge as desired) that uses symbolic modeling and is aimed at enhancing recognition of and HF self-care response actions to new or worsening dyspnea, fatigue and edema danger signs, (a) *reduces all-cause and HF-related healthcare resource utilization (HCRU)*, (b) *improves perceptions of dyspnea and fatigue*, and (c) *improves self-efficacy for managing symptoms*. Learning the HCRU effects of

NCT-03657459

symbolic modeling video education that explains the most common HF danger signs (dyspnea, fatigue and edema) and provides practical actions to reduce danger signs is important, as the intervention is easy to deploy, uses standard HF self-care behavior expectations, and is practical to use in hospital and home environments.

It is important to learn the *time to the video intervention effect* on (a) HCRU outcomes and (b) perceptions of fatigue, dyspnea and self-efficacy for managing HF symptoms. The intervention may have an early effect (30-days) that wanes over time, have a steady effect over a 6-month period, or the effect may be slow to peak (i.e., 90 or 180 days) as patients may learn through a recognition and self-care action “trial and error” approach.

Finally, the video intervention effect on outcomes may differ based on *after hospital discharge viewing by patients and/or family supporters*, as repeated viewing and/or family supporter viewing of danger signs and HF self-care actions may facilitate *earlier recognition* of warning signs and/or *earlier or more accurate adherence* to HF self-care actions that lead to improved HCRU outcomes, lower perceptions of fatigue and dyspnea and improved self-efficacy for managing symptoms.

Study Purposes

The purposes of this study are to examine the effects of HF danger signs videos (1 each on dyspnea, fatigue and edema) that include 2 key features: (1) recognition of each danger sign and (2) common, simple, practical self-care actions known to reduce HF danger signs ([a] fatigue: recognizing that it may be due to dehydration and adhering to physical activity and exercise expectations; [b] dyspnea and edema: adhering to a low sodium diet and fluid intake limitations; [c] all 3: contacting a doctor when appropriate). Based on Bandura’s social cognitive theory symbolic modeling, video content is meant to increase self-efficacy for independently completing self-care actions when dyspnea, fatigue and/or edema are present.

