The following outcomes will be assessed:

PRIMARY

1. 30 ± 6 days *first occurrence* of post-discharge **HF-related** HCRU; defined as hospitalization, emergency department [ED] visits, death or cardiac transplantation/ ventricular assist device [VAD] implant-- individual components and combined),

SECONDARY:

2. 90- and 180-day ± 6 days *first occurrence* of post-discharge **HF-related** HCRU; defined as hospitalization, emergency department [ED] visits, death or cardiac transplantation/ ventricular assist device [VAD] implant-- individual components and combined),
3. 30-, 90- and 180-day ± 6 days *first occurrence* of post-discharge **all-cause** HCRU; defined as hospitalization, emergency department [ED] visits, death or cardiac transplantation/ ventricular assist device [VAD] implant-- individual components and combined),
4. 30-, 90- and 180-day ± 6 days *time to* first occurrence of **all-cause** and **HF-related** post-discharge HCRU (individual components and combined),
5. 30-, 90- and 180-day ± 6 days *total all-cause* post-discharge HCRU (individual components and combined);
6. 30-, 90- and 180-day ± 6 days *total HF-related* post-discharge HCRU (individual components and combined);

NCT-03657459

7. Change in *functional status* from baseline to 30-, 90- and 180-days \pm 6 days after hospital discharge,
8. Change in *dyspnea scores* from baseline to 30-, 90- and 180-days \pm 6 days after hospital discharge,
9. Change in *fatigue scores* from baseline to 30-, 90- and 180-days \pm 6 days after hospital discharge, and
10. Change in *self-efficacy for managing symptoms* from baseline to 30-, 90- and 180-days \pm 6 days after hospital discharge
11. Differences in primary and secondary outcomes (1-10) among *intervention-group participants*, after creating 3 sub-groups based on post-discharge video viewing ([a] total number of times videos were watched, [b] viewed by caregivers/family in the hospital, and [c] viewed by caregivers/family post hospital discharge.

Specific aims and hypotheses:

1. Determine the effects (and time to effects) of HF danger signs education on *first occurrence*, *time to first occurrence* and *total* all-cause and HF-related HCRU after hospital discharge: hospitalization, ED visit, death, cardiac transplantation or VAD.
2. Examine if functional status, dyspnea, fatigue and self-efficacy for managing symptoms scores change over time and the direction of change.

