Hypothesis 3c: Repeat viewing of videos by patients, compared to 1-time viewing in-hospital and/or viewing of videos by family supporters/caregivers in hospital and/or post discharge, compared to viewing only by patients, will be associated with *higher self-efficacy for HF self-care actions* (due to symbolic modeling of self-care actions)

METHODS

Design: The study will use a 2-group, randomized, placebo-controlled, single blinded, design. Healthcare providers and unit nurses will be blinded to group assignment, but may learn about HF danger signs education if they enter the patients' room during intervention delivery or discuss the intervention prior to hospital discharge.

In brief, the research intervention involves 3 novel short videos (fatigue, dyspnea and edema) that will be viewed back-to-back by intervention group patients using a DVD player. Wellflix, Inc. videos are research-informed, use behavioral-modeling, are personally-tailored and are available 24/7 online. Patients will receive a handout sheet with the web address to view the videos after discharge and will be encouraged to view them with family members.

Sample (including sample size calculation) and Setting

A total of 732 patients will be enrolled (366 per group) and consist of adults with chronic HF (diagnosis \geq 2 months) who are hospitalized for acute decompensated HF within Cleveland Clinic Hospitals. This sample size includes a 10% attrition rate. Sample size was based on power calculations using 30-day first occurrence of HF-related HCRU (hospitalization, emergency department visit, mortality, cardiac transplantation or VAD). The current expected 30-day HF-related readmission rate is 20% among the control group. Allowing for other HCRU components, a control group HCRU rate of 28% is expected at 30 days. At 90 days, HCRU rate of 46% is expected in the control group. Sample size calculations were performed using SAS software (version 9.4; Cary, NC) and assume use of two-sided Pearson -chi square tests. With 329 patients in each group there will be 80% power to detect a 33% relative decrease (9.2% absolute decrease) in first occurrence of HF-related HCRU from a HCRU rate of 28% in the control group. With this sample size there would also be 85% power to detect a relative decrease of 25% (absolute decrease of 11.5%) from a control group event rate of 46% at 90-days. Allowing for 10% loss to follow-up, we will enroll 366 patients per group (732 total).

NCT-03657459

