Patients will have decompensated HF with preserved or reduced ejection fraction when hospitalized and New York Heart Association FC III or ambulatory IV symptoms. Diagnosis and etiology of HF will be confirmed in the electronic medical record prior to enrollment.

Inclusion Criteria:

1. Not referred for cardiac transplantation or ventricular assist device placement during the index hospitalization (OK to be assessed for future placement),
2. Minimum age 18 years (no upper age limit),
3. Cognitively intact and able to view videos (adequate eyesight and hearing) with correction, if needed,
4. Discharge to home, assisted living facility or to a family member's home and can control dietary sodium and fluids as needed,
5. Willing to participate; which may require up to three (3) follow-up telephone calls post-discharge.

Exclusions:

1. Chart documented psychiatric or cognitive conditions that limit ability to understand video content or adhere to self-care recommendations (Alzheimer's condition, dementia, schizophrenia, other neurological history that impairs memory or concentration),
2. Plans to discharge to skilled nursing facility or hospice care,
3. Receiving home hospice or palliative care; or has a medical condition reflecting less than 1 year of survival (cachexia, end stage liver disease or cancer or non-ambulatory New York Heart Association functional class IV HF),
4. Hospitalized but at admission, in New York Heart Association functional class I or II HF
5. Post-cardiac transplantation or ventricular assist device placement,
6. Currently enrolled in another experimental HF research study,
7. Chronic renal failure and receiving chronic hemodialysis therapy for an estimated glomerular filtration rate $< 15 \text{ mL/minute/1.73 m}^2$,
8. A non-traditional form of HF (hypertrophic or restrictive forms of cardiomyopathy, congenital heart disease or Takotsubo cardiomyopathy).

Intervention

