The fatigue and dyspnea video's will be viewed back-to-back and the edema video will be added for patients with a history of edema. There are 4 versions of each video: (1) based on race (Caucasian and African-American) and sex (male and female)—to promote symbolic modeling— by patients who look like video models (as stated in the introduction). Scripts for each video were developed jointly by [name], Director of Media and Education for Wellflix, Inc. and [name] PhD, principal investigator and clinical nurse specialist in HF. Content includes recognition and assessment of fatigue, dyspnea and edema and specific actions to take to reduce the danger signs or prevent worsening (dietary sodium and/or fluid restriction, physical activity/exercise and contacting the doctor).

Overall video viewing time for all 3 videos is 9:50 minutes; the fatigue and dyspnea videos that all intervention patients will view are 6:50 minutes:

- *Fatigue* is 2:20 minutes + end text list= 3:00 minutes;

NCT-03657459

- *Dyspnea* is 1:40 minutes + dyspnea “yes” or “no” management (2 options; patient selects the option that matches current status) = 3.50 minutes
- *Edema* is 2:40 minutes + end text list= 3:00 minutes;

During hospitalization, videos will be loaded into an iPAD and will be viewed through the iPAD.

Patients have an opportunity to view videos post-discharge as desired and able. *Post discharge*, videos can be in 2 ways: (1) via the Wellflix, Inc. site at www.wellflix.net/DangerSignsCC or (2) by DVD player (DVD created by Wellflix, Inc for this research), for patients who have DVD player capability and prefer this method.

NOTE, at/after 180-day follow up data are collected, *usual care group* patients will be offered access to Wellflix, Inc. videos used in this research study via mailing of a handout sheet developed specifically for them (that contains the web address and a note of encouragement to view the videos.

Outcomes and Measurement

HCRU. Includes all-cause and HF-related hospitalization, ED visit, death, cardiac transplantation, or VAD placement at 30-, 90-, and 180-days \pm 6 days in both groups. Data will be retrieved from medical records when available or via telephone call to patients.

- Patients will receive a calendar to keep track of HCRU events in-between phone calls.
- Research nurses will use a case report form to record HCRU events

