After completing baseline paperwork, patients will be randomly assigned to the usual care or usual care plus HF danger signs video education group using block randomization; with blocks of 20, to decrease the influence of external factors that could alter outcomes. The randomization assignment will be made by a QHS statistician.

After randomization to groups:

- Intervention group patients will receive usual hospital care and also, HF danger signs education via iPad by research personnel. Danger signs education can be administered at the time of enrollment. There is no need to wait until day of discharge, since HF danger sign messages are not individualized and discharge is a very busy time. Immediately prior to discharge, patients' focus may be on preparing to leave the hospital and not on education about HF, especially if patients believe that they have accurate perceptions of HF danger signals, even though in previous research, most subjects did not.
- Usual care group patients will be educated by their healthcare providers (including nurse/other caregivers). Education may include Elsevier HF videos that are shown on Cleveland Clinic hospital televisions.

A research nurse will use telephone calls or mailing methodologies to have the following 4/5 tools (40/43 items in total for usual care and intervention groups, respectively) completed at 30 ± 6 days: functional status, dyspnea, fatigue, self-efficacy for managing symptom and video watching experiences. Administration of functional status, dyspnea, and fatigue questionnaires will be randomly ordered (counterbalanced). The intervention-only group survey on video watching experiences will be administered last. It is expected that data collection will take ~ 10 minutes or less.

A research nurse will review EMRs of enrolled patients after the index (baseline) hospital discharge and at 30-, 60-, 90- and 180-days (± 6 days) for HCRU events.

- If not found in the EMR, telephone calls will be made to gather data.
- At baseline, research nurses will obtain home telephone number and the telephone number of a close relative or friend that can provide patient contact information, as needed.

NCT-03657459

Analyses

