Patient characteristics will be summarized overall and by randomized group using frequencies and percentages for categorical factors and means and standard deviations for continuous measures. First occurrence HCRU use (**all-cause and HF-related**) will be compared using Pearson chi-square tests. Time to first HFCU use will be summarized using Kaplan-Meier estimates, and compared using log-rank tests and Cox proportional hazards models. Total HCRU use will be compared using Poisson regression models. Linear mixed effect models will be used to evaluate trends in functional, dyspnea, fatigue, and self-efficacy measures over time and, if trends significantly differ, comparisons within time point will be performed. Secondary analyses will use similar methods to compare patients in the video group, stratified by video viewership, on the same outcomes. If appropriate, exploratory analyses will also be performed, comparing the above outcomes between treatment groups, adjusting for any patient characteristics that differ between randomized groups. Analyses will be performed using SAS software (version 9.4; Cary, NC), and an overall significance level of 0.05 will be assumed for all endpoints. Comparisons between the 3 subgroups of patients in the video group will use Bonferroni corrected significance criteria to preserve the overall error rate when making multiple comparisons.

Feasibility

The main campus of Cleveland Clinic has a high volume of HF discharges each year. Other hospitals in the system have moderate volumes of HF discharges, and are less likely to have patients who meet exclusion criteria due to enrollment in another research study or non-ambulatory NYHA FC IV (advanced) HF. Electronic medical records allow for review of data on events that occur in *all* system hospitals and regional medical practice ambulatory care sites; decreasing the need to rely on patient recall of HCRU.

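### Does the opening summary's wider list of HCRU events leave the primary endpoint undefined?

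*Combined protocol and SAP*

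**What the plan says.** The opening summary introduces HCRU in a background sentence about what unrecognized danger signs may lead to. Besides emergency care and hospitalization, its parenthetical lists "death/ventricular assist device/cardiac transplantation referral or placement, or an unscheduled/urgent office visit". Later in the same paragraph, 30-day HF-related HCRU is named as the primary endpoint with no further component list.

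The working sections use a shorter list:

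- **Study Purposes, primary outcome 1:** first HF-related HCRU at 30 ± 6 days, "defined as hospitalization, emergency department [ED] visits, death or cardiac transplantation/ ventricular assist device [VAD] implant-- individual components and combined".
- **Specific aims, aim 1:** the same components.
- **Sample (including sample size calculation) and Setting:** "Sample size was based on power calculations using 30-day first occurrence of HF-related HCRU (hospitalization, emergency department visit, mortality, cardiac transplantation or VAD".
- **Outcomes and Measurement, HCRU paragraph:** hospitalization, ED visit, death, transplantation or VAD placement. Directly below this comes the recording instruction: "Research nurses will use a case report form to record HCRU events".

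Three other statements bear on whether the extra components could arise. Inclusion criterion 1 reads "Not referred for cardiac transplantation or ventricular assist device placement during the index hospitalization (OK to be assessed for future placement". Feasibility says electronic records cover events in all "system hospitals and regional medical practice ambulatory care sites; decreasing the need to rely on patient recall of HCRU". Study Purposes lists "contacting a doctor when appropriate" among the self-care actions taught in the videos.

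**The concern.** The acronym carries the primary endpoint, and the one place that spells it out on first use gives a wider list than the outcome section. No sentence states that one list overrides the other. Both extra components could occur. A patient under assessment for a future transplant or VAD could be referred after discharge, and office visits could be visible in the ambulatory records.

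Office visits matter most, because they lie on the intervention's own pathway. If the videos lead a patient to an urgent office visit instead of the ED, that patient is event-free under the outcome section but has an event under the summary. The same success would be scored in opposite ways. In a first-occurrence composite, the choice of list could alter the event rate, the power and possibly the result. If events really were classified from the summary, the planned 28% control rate would no longer describe the endpoint being analysed.

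**Working it through.** **1. The component lists side by side**

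| Place | Hospitalization, ED, death, transplant/VAD | Transplant/VAD referral | Urgent office visit |
|---|---|---|---|
| Opening summary (background parenthetical) | yes | yes | yes |
| Study Purposes, primary outcome 1 | yes | no | no |
| Specific aims, aim 1 | yes | no | no |
| Sample-size basis | yes | no | no |
| Outcomes and Measurement | yes | no | no |

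Four statements agree, and one parenthetical differs. Of the five, the entry under Study Purposes is labelled primary and worded as a definition. The instruction about the case report form is a bullet under the measurement definition, so the events it refers to are those named just above it.

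**2. The planned figures belong to the narrower list**

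Inputs: control rate p1 = 0.28, relative decrease 33%, two-sided Pearson chi-square and 10% loss (sample-size section); alpha 0.05 (Analyses).

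- p2 = 0.28 × (1 − 0.33) = 0.1876; mean p̄ = (0.28 + 0.1876)/2 = 0.2338.
- Null term: √[2 × 0.2338 × 0.7662] = 0.5986.
- Alternative term: √[0.28 × 0.72 + 0.1876 × 0.8124] = 0.5950.
- n = [(1.960 × 0.5986 + 0.8416 × 0.5950)/0.0924]² = 328.2, so 329 per group, as stated.
- Power at 329: z = (0.0924 × √329 − 1.960 × 0.5986)/0.5950 = 0.845, so power = 80.1%.
- Enrolment: 329/0.9 = 365.6, so 366 per group and 732 in total, as stated.
- The 90-day figure also reproduces: 46% against 34.5% at 329 per group gives 85.4% (stated: 85%).

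**3. What the wider list would do (illustration only)**

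The documents give no rate for referrals or urgent office visits. Assume they add 6 points in usual care, so the control rate is 28% + 6% = 34%. Same formula, 329 per group:

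| Assumption for the video arm | Video-arm rate | Power |
|---|---|---|
| 33% relative decrease holds for the whole composite | 22.78% | 89.3% |
| adds 5 points | 23.76% | 82.7% |
| adds 6 points | 24.76% | 74.1% |
| adds 8 points | 26.76% | 52.4% |
| adds 10 points | 28.76% | 30.4% |

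In the other direction, adding only 2 points (20.76%) gives about 97%. With control rates of 30% and 38% as well, and the video arm between 1 point fewer and 4 points more than control in added events, the range is 29% to 93%. That spread is set by the grid chosen. It describes an endpoint that the methods do not specify.

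**4. Would anyone count the extra events?**

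It would take a nurse or analyst who passed over the outcome, sample-size and measurement sections and worked from the summary's background sentence. The sentence in Feasibility describes what the records can reach and does not tell staff to capture office visits. The inclusion criterion concerns eligibility and defines no event. Nothing in the methods says that referrals or office visits are recorded.

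**5. The 60-day time point**

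The summary names 60-day HCRU, and Data Collection schedules it: "A research nurse will review EMRs of enrolled patients after the index (baseline) hospital discharge and at 30-, 60-, 90- and 180-days". Feasibility mentions it too, while the outcome list and Outcomes and Measurement have only 30, 90 and 180 days. This is a collection point with no listed outcome attached. It does not touch the 30-day primary endpoint.

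**The case for a change.** The strongest case for acting is that a primary endpoint should have exactly one definition, fixed before events are classified, and that the correction is nearly free. The Introduction supports the pathway argument. In a cited report, 92% of patients responded to worsening symptoms by going to an ED and only 17% called their doctor, so moving patients from the ED to the office is a plausible effect of the videos. The case report form is not among the documents, so its match to the outcome section cannot be confirmed.

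Part of this stands. The two lists do differ, and nothing says in terms that the outcome section prevails. The direction of any effect on office visits cannot be settled from the documents.

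What does not stand is the step from a wording mismatch to an ambiguous endpoint. A protocol does not ordinarily need a clause saying that its outcome section overrides its summary. Nor is the recording instruction free-floating, since it follows its own definition. The pathway argument shows why including office visits would be a consequential design decision. It does not show that the plan has made that decision. An unseen form is not evidence of a wrong one.

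**Conclusion.** The concern does not hold as a fault in the plan. The summary's parenthetical is a clerical slip, contradicted by four mutually consistent statements, one of which is the labelled definition of the primary outcome. The operative composite is hospitalization, ED visit, death and transplant or VAD. The 28% control rate, 329 per group and 732 in total belong to it and reproduce at 80.1% power. The effect on the planned primary analysis is nil. The 29% to 93% range for the wider list rests wholly on assumed rates and carries no weight here.

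This conclusion assumes that the case report form follows the measurement section under which it is described and that analysts work from the listed outcomes, as is usual. Tidying the summary, or the unlisted 60-day time point, would be harmless editing but would change no result or conclusion.

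### Does writing the primary outcome as 30 ± 6 days, with no event-date cut-off and no rule for early loss, put the 30-day comparison at risk?

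*Combined protocol and SAP*

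**What the plan says.** The abstract states: "The primary end-point is 30-day HF-related HCRU". The section on sample size agrees: "Sample size was based on power calculations using 30-day first occurrence of HF-related HCRU". It expects 28% in the control group at 30 days, and adds "At 90 days, HCRU rate of 46% is expected in the control group". Hypothesis 1a is also worded for 30 days without a window.

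The list of outcomes under Study Purposes writes the primary as "30 ± 6 days *first occurrence* of post-discharge HF-related HCRU; defined as hospitalization", then ED visit, death, and transplant or VAD. The ± 6 days also stands on every secondary outcome, including the changes in functional status, dyspnea, fatigue and self-efficacy.

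Under Outcomes and Measurement, HCRU "Includes all-cause and HF-related hospitalization, ED visit, death, cardiac transplantation, or VAD placement at 30-, 90-, and 180-days", again with ± 6 days, and "Patients will receive a calendar to keep track of HCRU events in-between phone calls". Data Collection applies the window to the 30-day questionnaires and to the EMR reviews at 30, 60, 90 and 180 days.

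The Analyses section compares first occurrence by Pearson chi-square, and time to first use by Kaplan-Meier, log-rank and Cox. On loss, the plan says "Allowing for 10% loss to follow-up, we will enroll 366 patients per group (732 total", and Limitations promises intent to treat. On blinding: "Healthcare providers and unit nurses will be blinded to group assignment". Research personnel, who deliver the videos and collect the data, are not on that list.

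**The concern.** Read literally, one patient could be at risk of being counted for 24 days and another for 36. A chi-square test takes no account of time at risk. If record reviews closed later in one arm, that arm would gather extra events with no treatment effect, and the staff doing the reviews know the allocation.

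Loss raises a second question. The power calculation rests on 329 per group, which suggests that lost patients are left out. Intent to treat suggests that all 366 count. A rule picked after the data are seen could move the primary estimate. At stake would be a biased 30-day result, in a trial built to detect 9.2 points.

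**Working it through.** **Step 1. The plan's own figures.** Inputs from the sample size section: control 28%, relative decrease 33%, two-sided Pearson chi-square, 329 per group; the 0.05 level comes from Analyses. With p1 = 0.28, p2 = 0.28 × 0.67 = 0.1876 and mean p = 0.2338:

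n = [1.96·√(2·p(1−p)) + 0.842·√(p1(1−p1) + p2(1−p2))]² / (p1−p2)² = 328.2, so 329 per group, with power 80.1%. Using 18.8% instead gives 332, and 79.7% power at 329. Inflation: 329/0.9 = 365.6, so 366 per group and 732 in total. At 90 days, 46% versus 34.5% gives 85.4%. The sizing is right for a fixed 30-day risk.

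**Step 2. Events around day 30.** The plan gives 28% at day 30 and 46% at day 90. A constant hazard would give 1 − 0.72³ = 62.7% at day 90, so I use a Weibull curve (an assumption) through both points:

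F(t) = 1 − exp[−0.3285·(t/30)^k], where 0.3285 = −ln 0.72, 0.6162 = −ln 0.54, and k = ln(0.6162/0.3285)/ln 3 = 0.573.

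F(24) = 25.1% and F(36) = 30.6%. Per 366 controls, 366 × (0.2800 − 0.2511) = 10.6 first events fall on days 25–30, and 366 × (0.3056 − 0.2800) = 9.4 on days 31–36.

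**Step 3. Literal reading, same timing in both arms.** Averaging F evenly over days 24 to 36 gives 27.9%; times 0.67 this is 18.7%. Power at 329 per group is 80.0%. At the extremes, everyone closed at day 24 gives 25.1% versus 16.8% and 74% power; everyone closed at day 36 gives 30.6% versus 20.5% and 84% power. With no true effect the arms stay equal throughout, so there is no bias.

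**Step 4. Literal reading, timing that differs by arm.** No true effect, closing dates centred on day 30, 329 per group:

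| Assumed gap in mean closing date | False difference | Type I error |
|---|---|---|
| 1 day, F(30.5) − F(29.5) | 0.5 points | 5.2% |
| 3 days, F(31.5) − F(28.5) | 1.4 points | 6.7% |
| 6 days, F(33) − F(27) | 2.7 points | 12.1% |

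**Step 5. Loss before day 30.** The allowance is 366 − 329 = 37 per arm. Assume that all loss falls uniformly over days 0–30, unrelated to risk; the average of F over that span is 0.186. With L the fraction lost:

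- Lost counted as no event: rate = (1−L)·0.28 + L·0.186.
- Event-free lost dropped: the same numerator over (1−L) + L·0.186.

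| Loss, control vs video (no true effect) | Counted as no event | Dropped |
|---|---|---|
| 10% vs 10% | 27.1% vs 27.1%; error 5% | 29.5% vs 29.5%; error 5% |
| 8% vs 12% | 27.2% vs 26.9%; error 5.2% | 29.1% vs 29.8%; error 5.4% |
| 5% vs 15% | 27.5% vs 26.6%; error 5.9% | 28.7% vs 30.3%; error 7.4% |

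Errors are normal approximations. A simulation of 6,000 runs that also assumed 2% non-HF death gave 6.0% and 7.8% for the last row, and 4.7% and 4.8% for the first. With equal 10% loss and the planned effect, power is 82% to 83% under either rule. The last row needs 0.15 × 366 = 55 lost in one arm, against the plan's 37.

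**The case for a change.** The strongest case is that the plan does not rule the bias out. The research staff who show the videos also record events and review the charts, and they are not described as blinded. Only the video group answers an extra survey at the 30-day contact, so contacts already differ a little by arm. The EMR covers the health system's own hospitals and practices; an outside event in a patient who cannot be reached might be scored as unknown or as none. The two simple loss rules also err in opposite directions. Under 5% versus 15% loss they lie 0.9 + 1.6 = 2.5 points apart, which is not trivial against 9.2.

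What stands is that the text omits a cut-off and a loss rule, and that unblinded collection deserves care in its own right. What does not stand is the step from there to a threatened result. One review schedule applies to both arms, and nothing suggests that staff would shift dates by allocation. A review at day 24 does not close the record, since the EMR is read again at 60, 90 and 180 days and events carry dates. For loss, the plan has telephone back-up and a relative's number, and a patient who stops answering calls can still have a known day-30 status in the EMR. The opposite signs also mean that no particular direction of bias has been shown.

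**Conclusion.** No change follows; this is missing detail that analysts would fill sensibly. Every place that names or sizes the endpoint says 30 days. The ± 6 days also sits on questionnaire scores, where it can only mean assessment timing. Dated events let the analyst apply day 30 directly, and the 329-per-group sizing already points to leaving lost patients out of the chi-square.

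Followed even literally, with one schedule and similar loss in both arms, the primary test keeps type I error at about 5% and power at about 80%. Harm needs a difference between arms that the documents do not suggest: 1.4 points of false difference for a 3-day gap in closing dates, or 0.9 to 1.6 points for 5% versus 15% loss. At 8% versus 12% loss the error stays near 5%.

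An added cumulative-incidence analysis would gain little, because Kaplan-Meier estimates of time to first HF-related event at 30 days are already planned and censor lost patients. Treating non-HF death as a competing event would also need a decision on which deaths count in the composite, and the outcome list does not spell that out.

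The figures rest on the Weibull curve through 28% and 46%, and on loss that is uniform over 30 days and unrelated to risk. If evidence emerged of review dates or loss that differ by arm, the point would need a fresh look.
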